## 11. DATA MANAGEMENT AND STATISTICAL ANALYSIS

### 11.1. Sample size

- Part A

The sample size will be determined by the number of patients included per dose level and the observed toxicities. Given that (i) a maximum number of two dose levels will be explored, (ii) a classical 3+3 design will be used and (iii) at least 6 patients need to be treated at the RP2D before the phase II part starts formally, between 3-12 evaluable patients will be included. Patients non-evaluable for DLT will be replaced as appropriate.

- Part B

The efficacy of Debio 1143 in combination with nivolumab will be assessed in each cohort using the Bayesian posterior probability with early stopping rules for futility. The primary efficacy endpoint will be the confirmed ORR based on RECIST v.1.1 and/or GCIG (Cohort 4, if applicable). Assuming a futility response rate of 5% below which the response is considered not clinically meaningful and a true response rate of 15% which is considered clinically meaningful, with a maximum sample size of 15 patients per cohort, a cohort will be declared successful if there is at least 80% probability that the true response rate is  $\geq 15\%$ , which corresponds to 4 responses or more. A cohort will be declared futile if there is sufficiently low probability (20%) that the true response rate exceeds 5%. The first futility assessment will be performed after the first 8 patients are assessed and the second one after 11 patients. Futility assessment will be performed using the unconfirmed responses.

The total sample size will be between 32 (if all cohorts are futile) and 60 evaluable patients (if none of the 4 cohorts is futile) and no patient replacement occurs.

### 11.2. Data management and handling

#### 11.2.1. Data capture, verification and validation

Data entry, verification and validation will be captured using an electronic data capture (EDC) system. EDC system is a web-based computerized system designed for the collection of clinical data in electronic format (electronic case report forms (eCRF)); accessed via an Internet URL link.

EDC system access (username and password) will be provided upon completion and confirmation of prerequisite training. Username and passwords are personal and confidential and must not be shared.

The Investigator and/or designee will accurately, completely, and in a timely manner enter the required study data into the eCRFs. One eCRF will be completed for each patient.

Validation of the eCRF data is performed by i) automatic EDC system checks and ii) other data review tools, such as data listings. Data validation may result in the generation of queries. A query is a request for further information or clarification which may lead to data change. All queries (automatic and manual) will be generated and tracked within the EDC system until resolution. Manual queries can be raised directly into the EDC system by the clinical study team depending on the assigned EDC role throughout the duration of the study.

CRA review, source data verification, is conducted on an ongoing basis and is confirmed in the EDC system. In general, the CRA review is focused on the quality and integrity of the eCRF data.

Data management review is conducted on an ongoing basis, includes the review of all automatic system generated queries and is confirmed in the EDC system. In general, data management review is focused on the completeness and coherency of the eCRF data, and also includes reconciliation of external data versus eCRF data.

Medical review is conducted on an ongoing basis. In general, this review is focused on the completeness and coherency of the safety data.

The EDC system audit trail captures all eCRF data related activities such as: data entry, data modifications, data verification, data lock, e-signature etc.

eCRF data will be extracted from the EDC system into SAS® on a periodic basis and at defined study timepoints for statistical analysis.

### **11.2.2. Missing data handling for statistical analysis**

For missing or partial AEs and concomitant medications dates, conservative conventions will be applied in order to assign the events to corresponding periods. AE will be considered as treatment emergent and the medications will be considered as concomitant if the missing/partial dates cannot definitively exclude the treatment period.

Dates of remote events (e.g., medical history) may be partially incomplete, as the day and/or month may be unknown. Any missing day will be replaced by the 15th and any missing month by June.

Imputation of missing data will be described in detail in the statistical analysis plan.

### **11.3. Handling of values below (or above) a threshold**

To derive PK parameters and for summary statistics (except for calculations involving logarithmic transformations), plasma levels reported as below the LOQ will be considered as 0 when they occur before the first quantifiable concentration. When a plasma level is below LOQ between two quantifiable concentrations within a dosing interval, it will be set to ½ LOQ.

For summary statistics where calculation involves logarithmic transformations (including geometric mean calculation), plasma levels below LOQ will be set to ½ LOQ.

For pharmacodynamics parameters and safety laboratory tests, values below or above the limit of detection will be substituted with the lower/upper limit of detection.

### **11.4. Handling of unscheduled assessments or retests**

The unscheduled assessments and the retests performed before the treatment start will be included in the definition of the baseline which is the last value before the treatment start between the planned assessments, unscheduled assessments and retests.

After treatment start, the unscheduled assessments and retests will be used only in the derivation of endpoints that are not related to a specific timepoint (e.g. worst laboratory parameter level on-treatment). In the timepoint analyses, the original/planned values will be used.

#### **11.4.1. Derived parameters and endpoints**

##### **11.4.1.1. Efficacy**

Patients without any new anticancer therapy or PD will be assessed for anti-tumor efficacy every 8 weeks (±1 week) during the first 10 cycles and then every 12 weeks (± 1 week) from Cycle 13 onwards until PD occurs or start of a new cancer treatment or end-of-life-care or until the end of the Main study period whichever occurs first. For patients who continue study treatment after the Main study period, tumor

response assessments will continue at the frequency of local institutional care practice until PD, start of any new anti-cancer therapy, death or EOT, whichever occurs first.

Response according to RECIST version 1.1 (38) or GCIG criteria (39) (Cohort 4 for RECIST non-evaluable patients) will be assessed in the efficacy and ITT populations. CR and PR must be demonstrated by objective tumor assessment (CT scan/MRI or CA-125 dosage) and confirmed 4 weeks later. All patients will have a CT scan/MRI or CA-125 dosage at the time of PD. Tumor response will also be assessed by using the novel modified RECIST v1.1 guideline for immunotherapeutics, iRECIST.(40) These exploratory analyses using iRECIST guideline will be presented in detail in the SAP.

In case of premature discontinuation with SD at the EOS visit, this SD will be included in the derivation of efficacy parameters only if the assessment has been performed at least 35 days after treatment start.

The start of a systemic new anti-cancer therapy without prior disease progression could potentially impact the tumor activity observed, hence potentially biasing the evaluation of Debio 1143 anti-tumor activity. As a consequence, no further efficacy data will be collected after the start of any new anti-cancer treatment, except for OS, at least until study data cut-off.

The confirmed response will be used in the primary ORR analysis while a secondary analysis will be performed using the unconfirmed response.

- **Objective response** is derived as any PR or CR recorded after the start of study treatment until disease progression/recurrence is documented, a new systemic anti-cancer therapy is started or analysis cut-off, whichever occurs first.
- **BOR** is the best response (CR, PR, stable disease or disease progression) recorded after the start of study treatment until disease progression/recurrence is documented, a new systemic anti-cancer therapy is started or analysis cut-off, whichever occurs first.
- **Disease control** is derived as any CR, PR or stable disease reported during the study
- **Duration of response** is the time from documentation of tumor response to disease progression, start of a systemic new anti-cancer therapy or analysis cut-off, whichever occurs first.
- **PFS duration** is defined as the time elapsed between treatment initiation and tumor progression or death from any cause, whichever occurs first. Censoring to the last assessment will be applied in the following situations: a) lost to follow-up, b) no progression before analysis cut-off, c) start of a new systemic anti-cancer therapy. The median PFS and the PFS rate at 6, 12 and 18 months will be derived from the Kaplan-Meier curves.
- **OS** is defined as the time elapsed between treatment initiation and death from any cause. In the main analysis, censoring to the last assessment will be applied in the following situations: a) lost to follow-up, b) alive at analysis cut-off. A sensitivity analysis will be performed by censoring the OS at the time of start of a new systemic anti-cancer therapy. The median OS and the OS rate at 12 months will be derived from the Kaplan-Meier curves.

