## 8.2. Study assessments

### 8.2.1. Efficacy

Tumors will be assessed according to either RECIST version 1.1 guidelines by CT scan or MRI imaging of the target/non target lesions (38), and/or GCIG criteria using the serum marker CA-125 for Cohort 4, if applicable.(39)

CT scan and MRI will be performed at screening, then every 8 weeks ( $\pm$  1-week tolerance window) during the first 10 cycles, then every 12 weeks ( $\pm$  1 week) from Cycle 13 until symptomatic PD or confirmed iRECIST PD or start of any new cancer treatment or end-of-life care or end of the Main study period, whichever occurs first. For patients who exceptionally continue study treatment after completion of 13 cycles, tumor response assessments will continue at 12-week intervals ( $\pm$  1 week window) until the end of the Main study period, and thereafter at the frequency of local institutional care practice until PD, start of any new anticancer therapy, death or EOT.

Imaging will be performed as per site standard but whenever possible using contrast agent at screening and during treatment

CA-125 dosages will be performed at screening exclusively in patients included in Cohort 4. In case of abnormally elevated levels before treatment start, these dosages will be repeated on Day 1 of each subsequent cycle.

In case of response, efficacy assessments will be repeated 4 weeks later after first documentation (+ 1-week tolerance window). All patients will have an efficacy assessment (CT scan/MRI or serum CA-125 dosage) at the time of disease progression and/or treatment discontinuation, whichever occurs first.

As an exploratory analysis, tumor response will also be assessed using the iRECIST criteria (novel modified RECIST v1.1 guideline for immunotherapeutics).(40) These exploratory analyses will be described in the SAP.

Patients with asymptomatic, but radiologically observed unconfirmed PD as per iRECIST, may continue the study treatment, upon both the Investigator's request and the Sponsor's agreement, until PD is confirmed as per iRECIST or symptoms occurs or Investigator/patient decision to withdraw treatment, whichever occurs first.

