17. EFFICACY OUTCOMES

17.1. PRIMARY EFFICACY

For the purposes on the analyses described below, PD could be clinical progression (as recorded on the “End of Treatment” eCRF) or radiological progression (as recorded on the “overall response – RECIST v1.1” eCRF). In case of premature discontinuation with SD at the end of study (EOS) visit, this SD will be included in the derivation of the categorical efficacy parameters only if the assessment has been performed at least 35 days after treatment start.

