17.2.1.2. Unconfirmed best overall response (uBOR)

The uBOR will be defined as the best response across all post-baseline tumour assessments that occur before the start of a new anti-neoplastic therapy. For example, a subject who has SD at the first assessment, PR at the second assessment, and PD at the last assessment has a BOR of PR. The order to obtain the BOR is the following: CR, PR, SD, PD, Not Evaluable (NE).

If a subject has no post-baseline tumour assessments, BOR will be NE.

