17.2.1.3. Confirmed best overall response (cBOR)

The cBOR will also be analysed. In this case, CR and PR need to be confirmed at a subsequent assessment, at least 4 weeks after the initial overall response assessment of CR/PR and before the start of a new anti-neoplastic therapy or administration of non-permitted concomitant medications. cBOR will be derived as described in the RECIST 1.1 guidance.

Overall response first time point	Overall response subsequent time point*	cBOR
CR	CR	CR
CR	PR	SD, PD or PR ^a
CR	SD	SD, if minimum criteria for SD duration met, otherwise PD
CR	PD	SD, if minimum criteria for SD duration met, otherwise PD
CR	NE	SD, if minimum criteria for SD duration met, otherwise NE
PR	CR	PR
PR	PR	PR
PR	SD	SD
PR	PD	SD, if minimum criteria for SD duration met, otherwise PD
PR	NE	SD, if minimum criteria for SD duration met, otherwise NE
NE	NE	NE

* Subsequent time point is not necessarily the direct subsequent scan (eg. PR-SD-PR will have PR as confirmed BOR)

^a If a CR is truly met at first time point, then any disease seen at a subsequent time point, even disease meeting PR criteria relative to baseline, makes the disease PD at that point (since disease must have reappeared after CR). Best response would depend on whether minimum duration for SD was met. However, sometimes ‘CR’ may be claimed when subsequent scans suggest small lesions were likely still present and in fact the patient had PR, not CR at the first time point. Under these circumstances, the original CR should be changed to PR and the best response is PR.

When SD is believed to be the best response, it must also be a minimum of 35 days after treatment day 1. If the

Document: T:\sas\Debiopharm\Debio_1143\CZA60507\Biostatistics\Documentation\SAP\SAP Text\5

Author: [REDACTED] Version Number: 5.0
Version Date: 19APR2022

Template No.: CS_TP_BS016 Revision 5
Effective Date: 01Apr2018

Reference: CS_WI_BS005

minimum time is not met, the subject’s best overall response depends on the subsequent assessments. For example, a subject who has SD at the first assessment, PD at the second assessment and does not meet the minimum duration for SD, will have a best overall response of PD. The same subject lost to follow-up after the first SD assessment would be considered NE for BOR.

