17.2.1.4. Disease control

Disease control is derived as an uBOR of CR, PR or SD recorded at any point during the study.

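### The 35-day minimum for stable disease is tied to a visit with no scheduled scan and is missing from the unconfirmed best response that defines disease control, so an early SD can count as disease control while confirmed best response is PD or NE

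*Protocol*

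**What the plan says.** The 35-day minimum appears in three places.

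- Protocol 11.4.1.1 introduces it for one situation: "In case of premature discontinuation with SD at the EOS visit, this SD will be included in the derivation of efficacy parameters". The full condition is that "this SD will be included in the derivation of efficacy parameters only if the assessment has been performed at least 35 days after treatment start".
- SAP 17.1 restates it with the same trigger: "In case of premature discontinuation with SD at the end of study (EOS) visit, this SD will be included in the derivation". There it governs the categorical efficacy parameters.
- SAP 17.2.1.3, on confirmed best overall response (cBOR), drops the trigger: "When SD is believed to be the best response, it must also be a minimum of 35 days after treatment day 1". Its worked example scores an early SD followed by progression as PD, and an early SD followed by loss to follow-up as NE.

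Two definitions carry no minimum. Unconfirmed best overall response (uBOR) in SAP 17.2.1.2 reads: "The uBOR will be defined as the best response across all post-baseline tumour assessments that occur before the start of a new anti-neoplastic therapy". It ranks SD above PD and NE. SAP 17.2.1.4 builds on it: "Disease control is derived as an uBOR of CR, PR or SD recorded at any point during the study". The protocol's own definition says that disease control "is derived as any CR, PR or stable disease reported during the study".

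On scan timing, the CT/MRI row of protocol Tables 1-1 and 8-6 is marked at screening, Cycle 2 Day 15, later cycles, EOT and follow-up, but not at EOS. The table notes and section 8.4 define EOS as the close of the Main or Extended study period. Section 8.2.1 also requires an efficacy assessment "at the time of disease progression and/or treatment discontinuation, whichever occurs first". SAP 7.4 brings unscheduled tumour assessments into all the efficacy analyses.

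**The concern.** The purpose of a minimum time is to stop a scan taken shortly after treatment start from being credited as disease stabilisation. Here the rule is attached to a visit at which no scan is planned. The one version free of that visit sits in a derivation that disease control does not use. The same patient can then be PD or NE on cBOR and a disease-control success on uBOR, and SAP 17.2.3.2 tabulates both. Disease control rate (DCR) is a secondary endpoint in both study parts. The error can only raise it, never lower it.

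**Working it through.** **Where 35 days comes from.** The documents give no derivation, but the figure matches the schedule.

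- First on-treatment scan: Cycle 2 Day 15 with 28-day cycles, so study day 28 + 15 = 43, which is 42 days after start.
- Window ±7 days: 42 − 7 = 35 to 42 + 7 = 49 days after start.
- On the every-8-weeks wording instead: 56 − 7 = 49 to 56 + 7 = 63 days.

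On either reading, every in-window scheduled on-treatment scan meets the minimum. The rule has work to do only for other scans.

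**EOT scan.** The visit is 30 ± 5 days after the last Debio 1143 dose. With the last dose on Day d, the scan falls d − 1 + 30 = d + 29 days after start at nominal timing, and d + 24 at the early edge.

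| Last dose, Day | Early edge | Nominal | Late edge |
|---|---|---|---|
| 1 | 25 | 30 | 35 |
| 5 | 29 | 34 | 39 |
| 10 | 34 | 39 | 44 |
| 15 | 39 | 44 | 49 |

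d + 29 < 35 requires d ≤ 5, and d + 24 < 35 requires d ≤ 10. An EOT scan in its window is therefore too early only if dosing stopped by about Day 5 to 10. EOT may also be brought forward before new therapy.

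**Three routes to an SD before 35 days.**

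1. A scan at discontinuation itself (protocol 8.2.1), with no later assessment. cBOR is NE; uBOR is SD; disease control is yes.
2. An EOT scan after a last dose by about Day 5 to 10, with no later assessment. Same result.
3. An unscheduled SD in a patient who continues and then has PD at the first scheduled scan. cBOR is PD; uBOR is SD; disease control is yes.

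If EOS is read as EOT, SAP 17.1 removes route 2, and route 1 where the scan is recorded as the EOT assessment. Route 3 stays open, because that patient did not discontinue with SD.

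**Effect on DCR.** One patient moves DCR by 1/n, with the denominator unchanged:

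- n = 8: 1/8 = 12.5 points
- n = 11: 1/11 = 9.1 points
- n = 15: 1/15 = 6.7 points

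As an illustration with exact 95% intervals, 3/15 is 20.0% (4.3 to 48.1) and 4/15 is 26.7% (7.8 to 55.1).

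**Effect elsewhere.** SD is not a response. The confirmed response rate, the futility boundaries (0 of 8; at most 1 of 11) and the 4-of-15 efficacy rule count responses only, so none changes.

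**The case against.** The strongest reply is that SAP 17.1 already covers this. It opens the efficacy section, speaks for the analyses that follow, and names the categorical parameters, which include uBOR and disease control. EOS may be a loose label: SAP 7.4 mentions both end of treatment and end of study as early-termination visits, and premature discontinuation with SD makes sense only for an individual patient. On that reading most early-discontinuation SDs already drop out of DCR. This stands in part, and it shrinks the gap. It does not close it, because an early unscheduled SD followed by PD in a continuing patient is outside the clause under any reading of EOS.

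The second reply is that the consequence is small. DCR is descriptive, no formal hypothesis is tested, cBOR is tabulated with it, swimmer plots show SD duration and all response data are listed. That also stands. It limits the weight of the point but does not remove the contradiction between two derivations in one SAP.

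A reader might infer that anyone who stops in the first three weeks with SD is credited. The schedule does not support that. With an in-window EOT scan, a last dose from Day 6 passes 35 days at nominal timing, and from Day 11 even at the early edge. Such patients are exposed only through a scan at discontinuation, a brought-forward EOT or an unscheduled scan.

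**Conclusion.** The point holds as a limited inconsistency. As written, an SD before 35 days can count as disease control while cBOR for the same patient is PD or NE. The trigger in protocol 11.4.1.1 and SAP 17.1 names a visit with no planned scan.

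The effect is confined to uBOR and DCR and can only be upward: 12.5, 9.1 or 6.7 points per patient at n = 8, 11 or 15. These sizes assume that the patient stays in the denominator and has no later SD or response. The documents do not say how many such patients there are, and there may be none. It may be tempting to assume one or two per cohort and quote a total inflation, but nothing in the plan supports a count. Nor should the point be read as bearing on the primary endpoint or on any stopping or efficacy decision.

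**What to change.** - In protocol 11.4.1.1 and SAP 17.1, replace the EOS clause with a rule that applies whatever the visit: an SD assessment made less than 35 days after treatment start does not count towards the categorical efficacy parameters.
- In SAP 17.2.1.2 and 17.2.1.4, state that such an assessment gives neither uBOR = SD nor disease control. Best response is then set by later assessments: PD if that is what they show, NE if there are none, as 17.2.1.3 already does.
- Leave the cBOR table in 17.2.1.3 as it is. It assigns SD to an unconfirmed CR or PR followed by PD or NE when the minimum duration is met, with no SD assessment at all. A blanket demand for an SD scan at 35 days or later would contradict it.

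The cost is a sentence in each place and one condition in the uBOR and disease-control program. No SD from an in-window scheduled on-treatment scan is lost. DCR stays the same or falls slightly.

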#### 11.4.1.2. Safety

A TEAE is any new, related or non-related, undesirable medical occurrence or change of an existing condition in a patient that occurs during the treatment-emergent period, starting or worsening on or after the first study drug administration and up to 5 months ( $\pm 15$  days) after last nivolumab infusion, or the earliest date of new anticancer therapy – 1 day, whichever occurs first.

#### 11.4.1.3. Pharmacokinetics

Based on sparse plasma concentrations, Debio 1143 and Debio 1143-MET1 PK parameters will be evaluated from the population PK disposition model available to date (36) via a population approach with nonlinear mixed effects modelling using NONMEM® (ICON Solutions). If appropriate, post-hoc estimates

of AUCs,  $C_{max}$  and  $C_{min}$  will be derived for Debio 1143 and Debio 1143-MET1. Inter- and intra-individual PK variability will be assessed by pooling data of this study with those of other clinical trials.

For nivolumab, serum concentration versus time profiles will be analyzed. If deemed appropriate, nivolumab concentrations will be integrated in a population PK model (37) to estimate relevant PK parameters.

These population PK analyses will be described in a separate analysis plan and reported separately.

If data allow, a non-compartmental PK analysis for Debio 1143 and Debio 1143-MET1 may also be performed using Phoenix™ WinNonlin® (Certara L.A.). As appropriate, this analysis will also be described in a separate analysis plan.

